2.2.2.1. Recommended Phase 2 Dose

The treatment dose for CTL-002 for the initial Phase 2a exploration is set at 10 mg/kg, to be administered Q2wk (applicable for all cohorts treated in combination with nivolumab) or 20 mg/kg Q3wk (for the cutaneous squamous-cell carcinoma cohort; CTL-002 treatment in combination with cemiplimab).

Pharmaco-modelling and obtained PK/pharmacodynamic data from Part A (Phase 1) indicate complete GDF-15 neutralization at the dose of 10 mg/kg and the dosing interval Q2wk or the dose of 20 mg/kg and the dosing interval Q3wk or Q4wk, respectively in serum and tumor vasculature (tumor microenvironment) in subjects with a wide range of baseline GDF-15 serum levels. In the current development phase (Phase 2a) the dosing interval follows for subject convenience the dosing interval of the checkpoint inhibitor. No safety events of concern and no DLT have been observed at any dose in Phase 1, including the doses of 10 mg/kg and 20 mg/kg. In addition, the for this initial Phase 2 exploration selected doses of 10 mg/kg and 20 mg/kg (with dosing interval of Q2wk and Q3wk, respectively) provide exposure that is still below the no-observed adverse effect level (NOAEL) in non-human primate (NHP).

Depending on further PK/pharmacodynamic data observed and safety and efficacy data, the SRC may modify these Phase 2 doses if seen as recommended or if a second dose is decided to be explored (all via substantial amendment).

2.3. Optional Stereotactic Radiotherapy

All subjects in the phase 2 part that achieve/maintain stable disease by week 24 but do not show tumor shrinkage beyond -10% as per RECIST criteria can undergo if desired by the treating physician and agreed by the patient stereotactic radiotherapy of one or more tumor lesions to increase neoantigen exposure and potential for response improvement (as was seen in two phase 1 patients). This should always be pre-discussed with the medical representative of the sponsor and the radiotherapy area should not include all lesions that are used for RECIST response assessment to allow for abscopal antitumor effect assessment.

Radiotherapy should be performed according to local hospital's regulations.

Note: In case of initiation of stereotactic radiotherapy in addition to study treatment, an optional tumor biopsy should be performed no earlier than 4 weeks after initiation of radiotherapy, if seen as safe and medically feasible by the treating physician.

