1.10.3. Exploratory Endpoints**Part A (Phase 1; dose escalation):**

- Evaluation of GDF-15 serum levels and their correlation with pharmacodynamic and clinical response
- Immune cell phenotyping including activation status and immune cell infiltration pattern in tumor tissue
- Molecular profiling (e.g., transcriptional profiling, mutational status, mutational burden of tumor tissue)
- To assess anti-tumor efficacy (PR, CR, DOR, PFS, and OS) of CTL-002 in combination with an anti-PD-1 checkpoint inhibitor using iRECIST ([Seymour et al., 2017](#)), criteria in solid tumors in subjects with advanced-stage solid tumors that relapsed post or were refractory to a prior anti-PD-1/PD-L1 therapy

Part B (Phase 2a; expansion):

- In subjects that undergo tumor biopsy: Immune cell phenotyping including activation status and immune cell infiltration pattern in tumor tissue
- In subjects that undergo tumor biopsy: Molecular profiling (e.g., transcriptional profiling, sequencing of genes of interest, mutational status, mutational burden of tumor tissue) and evaluation of GDF-15 levels
- To assess anti-tumor efficacy (PR, CR, DOR, PFS, and OS) of CTL-002 in combination with an anti-PD-1 checkpoint inhibitor using iRECIST criteria ([Seymour et al., 2017](#)), in solid tumors that relapsed on or were primary refractory to a prior anti-PD-1/PD-L1 therapy
- To assess in subjects with advanced-stage cutaneous squamous-cell carcinoma that relapsed on or were primary refractory to a prior anti-PD-1/PD-L1 therapy: the anti-tumor efficacy (PR, CR, DOR, PFS, and OS) of CTL-002 in combination with cemiplimab checkpoint inhibitor using WHO bidimensional measurements
- The proportion of subjects with tumor shrinkage, a confirmed partial PR and/or CR, and ORR after receiving stereotactic radiotherapy according to RECIST V1.1 (ORR-2)
- The interval between application of stereotactic radiotherapy and first documented evidence of a PR or CR according to RECIST V1.1 (TTR-2)
- The interval between the date of first documented evidence of PR or CR after having received stereotactic radiotherapy, until first documented evidence of disease progression or death, due to any cause according to RECIST V1.1 (DOR-2)

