- (c) For **melanoma, cutaneous squamous-cell carcinoma** and the **biomarker cohort with mixed solid tumors** (“basket” cohort), an additional **follow-up, on-treatment biopsy** is mandatory to assess for immunologic changes in the tumor. **Important note:** All biopsies are only taken if considered **safe** and **feasible** by the treating physician/Investigator.
- (d) All subjects that **achieve/maintain stable disease by week 24** but do not show tumor shrinkage beyond – 10% as per RECIST criteria can undergo if desired by the treating physician and agreed by the patient stereotactic radiotherapy of one or more tumor lesions to increase neoantigen exposure and potential for response improvement (as was seen in two Phase 1 patients). This should always be pre-discussed with the medical representative of the sponsor and the radiotherapy area should not include all lesions that are used for RECIST response assessment to allow for abscopal antitumor effect assessment.

Note: In case of initiation of stereotactic radiotherapy in addition to study treatment, an optional tumor biopsy should be performed no earlier than 4 weeks after initiation of radiotherapy, if seen as safe and medically feasible by the treating physician.

For the **third group** (biomarker cohort with mixed solid tumors; “basket” cohort) the following additional requirements and restrictions apply:

- (e) Up to **5 subjects** (but no more) in the PD-L1 TPS > 1 group with **tumor indications that are currently not yet approved at all for anti-PD-1/PD-L1 treatment** may be enrolled if treated with a currently approved anti-PD-1/PD-L1 (for other indication(s)), if also all other criteria for the group apply. For the PD-L1 TPS ≤ 1 group this may be up to 10 patients.
- (f) No subjects with melanoma (cutaneous, mucosal or uveal) can be enrolled into this cohort.

For all cohorts, response is defined as a subject presenting with a partial or complete response to treatment according to RECIST criteria.

If responses are seen and considered to be of interest by number and depth of response, the Safety Review Committee (SRC) may decide in agreement with the Sponsor to expand individual cohorts following a **Simon-2-stage design** to confirm a certain response rate with the following assumptions:

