8.3.3. Efficacy Analysis

Efficacy analyses will be based on the Efficacy Evaluable Analysis Set and will include summaries of confirmed PR/CR, ORR, DoR, PFS, TTR, and OS by dose level (Part A) or cohort (Part B). Tumor response will be evaluated according to institutional standards using RECIST V1.1 for solid tumors, as well as iRECIST criteria. The definitions of the response evaluation endpoints are as follows:

Table 10 Definitions of Response Evaluation (RECIST V1.1)

Duration of Response:	Duration of response will be measured from the time that measurement criteria are met for CR or PR (whichever status is recorded first) until the first date that PD or death is documented. This analysis will include subjects with overall best response being CR or PR only. Subjects who neither progressed nor died will be censored at the date of the last tumor assessment
Overall Response Rate	Overall response rate is defined as the percentage of subjects with a CR or PR as assessed by RECIST V1.1. A responder is defined as a subject experiencing either a CR or PR by these criteria. Subjects with no tumor assessment after the start of study treatment are to be considered as non-responders.
Progression Free Survival	Progression-free survival is defined as the length of time between first study drug administration and the date of the first occurrence of disease progression or death from any cause.
Time to Response	Time to response will be measured from the time of first study administration until the day of documented CR or PR (whichever status is recorded first). Subjects without response will be censored at the date of the last tumor assessment or the date of death.
Overall Survival	Overall survival is defined as the time from the study drug administration to the date of death, regardless of the cause of death. Subjects who were alive at the time of the analysis will be censored at the date the subject was last known to be alive. Subjects without follow-up assessment will be censored at the day of their last dose and subjects with no post-baseline information will be censored at the time of their first study drug administration.

Abbreviations: CR = complete response; PD = progressive disease; PR = partial response; RECIST = Response Evaluation Criteria in Solid Tumors

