12. APPENDICES

APPENDIX 1: RESPONSE EVALUATION CRITERIA IN SOLID TUMORS (RECIST) VERSION 1.1

The following paragraphs represent a reference to the RECIST criteria (Version 1.1). The complete criteria are available at <https://recist.eortc.org/recist-1-1-2/> and are included in the published RECIST document.

At baseline, tumor lesions/lymph nodes will be categorized as measurable or non-measurable.

For Part B, only subjects with obvious measurable disease at baseline should be included in the present clinical trial.

A 1.1 Measurability of Tumor Lesions at Baseline – Definitions

Measurable disease – the presence of at least one measurable lesion. If the measurable disease is restricted to a solitary lesion, its neoplastic nature should be confirmed by cytology/histology.

Measurable lesions – *tumor lesions* that can be accurately measured in at least one dimension (longest diameter to be recorded) as ≥ 20 mm with chest x-ray, and as ≥ 10 mm with CT scan or clinical examination (using calipers). Bone lesions are considered measurable only if assessed by CT scan and have an identifiable soft tissue component that meets these requirements (soft tissue component ≥ 10 mm by CT scan). *Malignant lymph nodes* must be ≥ 15 mm in the short axis to be considered measurable; only the short axis will be measured and followed. All tumor measurements must be recorded in millimeters (or decimal fractions of centimeters) by use of a ruler or calipers. Tumor lesions situated in a previously irradiated area, or in an area subjected to other loco-regional therapy, are usually not considered measurable unless there has been demonstrated progression in the lesion.

Non-measurable lesions – all other lesions (or sites of disease), including small lesions are considered non-measurable disease. Bone lesions without a measurable soft tissue component, leptomeningeal disease, ascites, pleural/pericardial effusions, lymphangitis cutis/pulmonis, inflammatory breast disease, lymphangitic involvement of lung or skin and abdominal masses followed by clinical examination are all non-measurable. Nodes that have a short axis < 10 mm at baseline are considered non-pathological and should not be recorded or followed.

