where known residual benign tumors can remain). When effusions are known to be a potential adverse effect of treatment (e.g., with certain taxane compounds or angiogenesis inhibitors), the cytological confirmation of the neoplastic origin of any effusion that appears or worsens during treatment when the measurable tumor has met criteria for response or SD is advised to differentiate between response or SD and PD.

A 1.3 Tumor Response Evaluation

All subjects will have their BEST RESPONSE from the start of study treatment until the end of treatment classified as outlined below. Refer to [Table 11](#) and [Table 12](#).

Complete Response (CR) – disappearance of all *target* and *non-target* lesions and normalization of tumor markers. Pathological lymph nodes must have short axis measures <10 mm (*Note: continue to record the measurement even if <10 mm and considered CR*). Tumor markers must have normalized. Residual lesions (other than nodes <10 mm) thought to be non-malignant should be further investigated (by cytology or PET scans) before CR can be accepted.

Partial Response (PR) – at least a 30% decrease in the sum of measures (longest diameter for tumor lesions and short axis measure for nodes) of target lesions, taking as reference the baseline sum of diameters. Non-target lesions must be non-PD.

Stable Disease (SD) – neither sufficient shrinkage to qualify for PR nor sufficient increase to qualify for PD taking as reference the smallest sum of diameters on study.

Progressive Disease (PD) – at least a 20% increase in the sum of diameters of measured lesions taking as references the smallest sum of diameters recorded on study (including baseline) AND an absolute increase of ≥ 5 mm. Appearance of new lesions will also constitute PD (including lesions in previously unassessed areas). In exceptional circumstances, unequivocal progression of non-target disease may be accepted as evidence of disease progression, where the overall tumor burden has increased sufficiently to merit discontinuation of treatment, for example where the tumor burden appears to have increased by at least 73% in volume (which is the increase in volume when all dimensions of a single lesion increase by 20%). Modest increases in the size of one or more non-target lesions are NOT considered unequivocal progression. If the evidence of PD is equivocal (target or non-target), treatment may continue until the next assessment, but on further documentation, the earlier date must be used.

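### The primary ORR and the Simon responder counts have no cut-off at on-study stereotactic radiotherapy, so partial responses first reached after irradiation count toward the activity of CTL-002 plus anti-PD-1

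*Protocol*

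**What the plan says.** **Who may be irradiated, and why.** Section 2.3 offers the option to Part B subjects who "achieve/maintain stable disease by week 24 but do not show tumor shrinkage beyond -10% as per RECIST criteria". They may receive "stereotactic radiotherapy of one or more tumor lesions to increase neoantigen exposure and potential for response improvement". The same section describes this as given in addition to study treatment. The field is limited only by "the radiotherapy area should not include all lesions that are used for RECIST response assessment to allow for abscopal antitumor effect assessment".

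**How response is counted.**
- Appendix 1, A 1.3: "All subjects will have their BEST RESPONSE from the start of study treatment until the end of treatment classified as outlined below".
- Section 2.1, for all cohorts and directly before the Simon rules: "response is defined as a subject presenting with a partial or complete response to treatment according to RECIST criteria". Section 8.1 repeats this.
- Section 8.3.3, Table 10, under overall response rate: "A responder is defined as a subject experiencing either a CR or PR by these criteria".

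**What the counts decide.** Sections 2.1 and 8.1 set these rules, each with a stated power of 80%:
- Bladder, hepatocellular, lung and melanoma cohorts: at least 1 of 14, then at least 4 of 27.
- Colorectal cohort: at least 1 of 10, then at least 4 of 29.
- Cutaneous squamous-cell cohort: at least 2 of 12, then at least 6 of 36.

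**What is reported separately.** Section 1.10.3 adds ORR-2, TTR-2 and DOR-2 as exploratory endpoints for response after radiotherapy. It does not say that these responses leave the primary ORR or the Simon count.

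**The concern.** The Part B primary objective is the antitumor activity of CTL-002 with an anti-PD-1 agent. A subject eligible for radiotherapy is not a responder at that point, so a later PR is normally a new response, obtained with a third treatment that is offered in order to improve response. If that PR enters the primary ORR, the estimate no longer describes the two-drug combination.

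The effect can also be purely local. A target lesion that is irradiated stays in the sum of diameters, because nothing removes it, and its shrinkage alone can carry the sum past the PR threshold.

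The final thresholds are small (4 or 6 responders), so a single such case matters for any cohort near its threshold.

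**Working it through.** **Inputs.** Stage sizes and thresholds come from 2.1 and 8.1. The PR threshold is a 30% decrease in the target-lesion sum (A 1.3). No null rate is given for the Simon cohorts. I assume a drug-only rate of 5% and show 10% as well; 5-10% is the background range that 8.1 quotes for the basket cohort only.

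**Formula.** With n1 subjects in stage 1, n in total, continuation at r1 or more responders and success at r or more:

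P(success) = Σ over x ≥ r1 of P(X1 = x) × P(X2 ≥ r − x), with X1 ~ Bin(n1, p) and X2 ~ Bin(n − n1, p).

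**Step 1: the plan's own figure.** At p = 20%, the 4/27 rule gives 80.7% and the 4/29 rule 80.1%. At p = 25%, the 6/36 rule gives 80.3%. The stated 80% reproduces for all three.

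**Step 2: false success without radiotherapy.** For 4/27 at p = 5%:
- X1 = 1: 0.3593 × 0.0245 = 0.0088
- X1 = 2: 0.1229 × 0.1354 = 0.0166
- X1 = 3: 0.0259 × 0.4867 = 0.0126
- X1 ≥ 4: 0.0042
- Sum: 0.0422, or 4.2%

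**Step 3: one post-radiotherapy responder in the final count.** If stage 1 was passed without that subject, this acts like lowering the final threshold by one. For 4/27 at 5%: 0.3593 × 0.1354 + 0.1229 × 0.4867 + 0.0259 + 0.0042 = 0.1385 (0.13854 unrounded), or 13.9%. For all rules:

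| Rule | 5%, none added | 5%, one added | 10%, none added | 10%, one added |
|---|---|---|---|---|
| 4/27 | 4.2% | 13.9% | 27.4% | 48.5% |
| 4/29 | 4.7% | 13.5% | 28.9% | 46.2% |
| 6/36 | 0.6% | 1.9% | 10.6% | 18.5% |

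**Step 4: a gain in the observed response rate.** Suppose radiotherapy adds 4 percentage points. This is an assumption; 1 of the 25 Part A subjects had a PR after irradiation (1.7.1), and 1/25 = 4%. If both stages are read with these responses included, p = 9% and the 4/27 rule succeeds with probability 21.5%.

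If the stage 1 gate is read before any radiotherapy, X1 ~ Bin(14, 0.05) must be at least 1. Each stage 1 non-responder then converts with probability 0.04/0.95, and stage 2 runs at 9%. The result is 17.5%. The protocol does not say when stage 1 is read, so the range is 17.5-21.5%. For 6/36 the corresponding figures are 3.5% and 7.2%.

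**Step 5: can local shrinkage alone give a PR?** If irradiated target lesions form a share f of the baseline sum and the rest do not change, they must shrink by 0.30/f. For f = 50% that is 60%; for f = 60% it is 50%. So a PR is possible with no change in any non-irradiated lesion.

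**The case against.** The strongest reply is that the protocol never says outright that post-radiotherapy responses belong in the primary ORR. It gives them their own exploratory objective and endpoints. In section 1.7.1 it lists the irradiated Part A subject under disease stabilization, apart from the three confirmed PRs. An SAP, not available here, might carry the rule. This shows an intention to report separately, and it stands as far as that goes. But the protocol itself fixes the responder, the response window and the thresholds, and none of these excludes the post-radiotherapy period. Reporting a response in ORR-2 does not take it out of the ORR.

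The size of the effect is also open to challenge, and here much of the objection stands:
- Radiotherapy uptake, conversion and the null rate are all assumed.
- The Part A case involved a non-target lesion (1.7.1) and a subject with progressing liver lesions (1.8.5), not the Part B setting of stable disease at week 24.
- A larger gain, such as 8 points from two Phase 1 subjects, is not well supported. Section 2.3 says two, but 1.8.4 says one and 1.8.5 describes one.
- At a 10% null the rules already pass often without radiotherapy.
- Section 8.1 calls the study explorative, and expansion is at the discretion of the Safety Review Committee and the sponsor. One responder changes the result only at the threshold.

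A reader might also infer that Table 10 lets unconfirmed responses count, because it omits the word. It does not: Table 10 refers to RECIST V1.1, and the primary endpoint, the opening of 8.3.3 and Appendices 1 and 2 require confirmation in this non-randomized trial.

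Nor does Appendix 1 contradict section 2.3 where it says "Tumor lesions situated in a previously irradiated area, or in an area subjected to other loco-regional therapy, are usually not considered measurable". That sentence concerns measurability at baseline and goes on to make an exception for lesions that have progressed. It is not a rule for lesions irradiated on study.

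**Conclusion.** The point holds. Followed as written, the plan puts a PR first reached after on-study radiotherapy into the primary ORR and into the 4/27, 4/29 and 6/36 counts, and it leaves irradiated target lesions in the sum of diameters. This follows from the definitions taken together, not from an explicit statement.

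At an assumed 5% drug-only rate, one added responder roughly triples the false-success probability of each rule, which stays small in absolute terms for 6/36. An assumed gain of 4 points gives 17.5-21.5% for 4/27. These figures illustrate sensitivity; they do not forecast how many subjects will be irradiated or respond. The final count and the ORR are exposed whatever the timing. A stage 1 decision taken before week 24 would be little affected.

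A reader might go on to ask for PFS to be censored at radiotherapy. The documents do not call for this, and because subjects are selected for radiotherapy by their disease course, such censoring could itself be informative.

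This should be fixed. It does not undermine the design as a whole.

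**What to change.** Add one rule to 2.1, 8.1 and Table 10:

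- For the primary ORR and all Simon counts, a responder has a CR or PR, confirmed as Appendices 1 and 2 already require, that was first documented before any on-study radiotherapy.
- Subjects irradiated without a prior response count as non-responders.
- Responses first documented after radiotherapy count only in ORR-2, TTR-2 and DOR-2. For these endpoints, irradiated lesions are left out of the sum of diameters.

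The cost is wording. Section 5.4.1 already has nondrug interventions recorded in the eCRF, and no treatment changes. The downside is that the primary ORR may be slightly lower.

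In the same edit, sections 5.4.1 and 5.4.3, which confine on-study radiotherapy to palliation, need to be reconciled with section 2.3.

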2.4. Follow-up

Following the Safety Follow-up Visit / End of Core Study Visit, subjects will be followed up with an Efficacy and Survival follow-up for response duration and survival every 3 months for 12 months (in Part A) and every 3 months for 24 months (in Part B). The follow-up will be performed by telephone contact or (e)mail.

3. SELECTION AND WITHDRAWAL OF SUBJECTS

Subjects must meet all of the inclusion criteria and none of the exclusion criteria before enrolling into the study. Under no circumstances can there be exceptions to this rule. Procedures for handling subjects who do not meet entry criteria but have been enrolled or started treatment with CTL-002 (and possibly checkpoint-inhibitor) in error are described in [Section 3.4](#).

